### 3. ENDPOINTS AND BASELINE VARIABLES: DEFINITIONS AND CONVENTIONS

#### 3.1. Primary Endpoint

- *Mean change from baseline on the 4SC as compared to placebo by Week 49.*

#### 3.2. Secondary Endpoints

- *Mean change from baseline as compared to placebo on function tests including, Forced Vital Capacity (FVC), Northstar Ambulatory Assessment (NSAA), range of motion (ROM), Performance of Upper Limb (PUL), 6MWD at Week 17, 33, and 49.*
- *Mean change from baseline as compared to placebo on the 4SC at Week 17 and 33.*
- *Mean change from baseline as compared to placebo on muscle strength by myometry at Week 17, 33, and 49.*
- *In subjects randomized to Sequence 1, mean change from baseline as compared to historical control (see [Section 6.2.1](#)) on functional tests including, 4SC, 6MWD, FVC, NSAA at week 97.*
- *In the pre-specified subset of subjects who have baseline 4SC <3.5 seconds, ≥3.5 seconds and ≤8 seconds, or >8 seconds, the mean change from baseline as compared to placebo on muscle strength by myometry and on function tests including, 4SC, FVC, NSAA, PUL, 6MWD at Week 17, 33 and 49.*

Within the Northstar Ambulatory Assessment (NSAA), the two timed function tests, Rise from Floor and Run 10 meters will be analyzed separately for summary tabulation along with the total NSAA score.

The forced vital capacity(FVC) has been collected as the best 3 values at each of the given visits. Only the single best value (maximum forced vital capacity) will be used to analyze the FVC assessment. The percent predicted FVC is provided on the case report form from the best FVC value.

#### 3.3. Other Endpoints

##### 3.3.1. PK Endpoints

Blood samples for PK analysis of PF-06252616 will be taken according to the Schedule of Activities in the protocol. As specified in the protocol, *Noncompartmental PK parameters were to be derived from serum PF-06252616 concentration data for the following subjects and visits.*

- *All subjects receiving active drug:  $C_{max}$ ,  $T_{max}$ , and  $C_{trough}$  for all visits with PF-06252616 dosing.*

- All subjects receiving active drug in Period 1 followed by placebo in Period 2 (Sequence 2): terminal  $t_{1/2}$  for Visit 19 (last dose in Period 1) using concentration data from samples collected during placebo treatment in Period 2.
- Subjects with additional PK sampling receiving active drug in Period 1:  $AUC_{\tau}$  and  $C_{av}$  for Visits 3, 9, and 15 (first dose of each dose escalation level);  $AUC_{\tau}$ ,  $C_{av}$ , and  $CL$  for Visits 7, 13, and 19 (last dose of each dose escalation level); for subjects in Sequence 2, also  $V_{ss}$  for Visit 19.

However, the elimination of the 6 hour time point in Amendment 2 may impact the estimation of  $C_{max}$  and  $T_{max}$ . Therefore in place of  $C_{max}$  and  $T_{max}$  the concentration at 2 hours ( $C_2$ ), the end of the IV infusion, will be reported for all subjects.  $C_{max}$  and  $T_{max}$  will be reported only for the subjects with additional PK sampling.

The predose and 2 hour concentrations which represent  $C_{trough}$  and  $C_2$ , respectively, will be summarized for each visit as part of the serum PF-06252616 concentration data. In addition,  $C_{trough}$  and  $C_2$  will be summarized as PK parameters for the last visit of each 16-week dose escalation level in Periods 1 and 2.

With these adjustments, the PK parameters to be determined are listed in the following table, with Visits identified by Week.

**Table 1. PK Parameters To Be Determined**

Subjects	Visit(s)	Parameter	Analysis Scale	PF-06252616
All Subjects	Weeks 13, 29, 45, 61, 77, 93 (Last dose for each dose escalation level in Periods 1 and 2) (Period 1 and Period 2)	$C_{trough}$	ln	D
		$C_2$	ln	D
Subjects in Sequence 2	Week 45 (Last dose in Period 1)	$t_{1/2}^a$	R	D
Subjects with additional PK sampling	Weeks 1, 13, 17, 29, 33, 45 (First and last dose for each dose escalation level in Period 1)	$C_{max}$	ln	D
		$T_{max}$	R	D
		$AUC_{\tau}$	ln	D
		$C_{av}$	ln	D
	Weeks 13, 29, 45 (Last dose for each dose escalation level in Period 1)	$CL$	ln	D
Subjects in Sequence 2 with additional PK sampling	Week 45 (Last dose in Period 1)	$V_{ss}^a$	ln	D

- Key: D = Displayed with descriptive statistics, ln = natural log transformed, R=raw (untransformed), a = if data permits.

### 3.3.2. PD Endpoints

- *Mean percent change as compared to placebo in thigh muscle volume as measured on MRI by Week 17, 33, 49. Within subject change from baseline in thigh muscle volume through Week 97.* Specifically, this will include the Whole Thigh Muscle Volume, which is a measure of the total contractile tissue volume within the thigh.

In addition, the Whole Thigh Muscle Volume Index will also be analyzed, which is the percent of the thigh that is contractile tissue vs total thigh muscle bundle where the thigh muscle bundle includes both contractile and non-contractile tissues (ie, muscle and inter/intra-muscular fat regions). Muscle Volume Index is derived as follows:  $((\text{muscle volume})/(\text{muscle volume} + \text{inter/intra-muscular fat volume})) * 100$ .

Both measures will use the entire thigh to determine muscle volume. Details of the thigh MRI measures are provided in the Study Imaging Review Charter.

- *Noncompartmental GDF-8 parameters such as  $AUC_{\tau(GDF-8)}$ ,  $C_{GDF-8(0)}$ ,  $C_{max(GDF-8)}$ ,  $T_{max(GDF-8)}$ ,  $C_{trough(GDF-8)}$ , and  $C_{av(GDF-8)}$ , may be determined.* Blood samples for PD analysis of GDF-8 (myostatin) will be taken according to the Schedule of Activities in the protocol. The protocol endpoints indicated that noncompartmental GDF-8 parameters *might* be determined. The planned parameters are  $C_{0(GDF-8)}$ , the baseline concentration (Day 1 predose); and  $C_{trough(GDF-8)}$ , the predose concentration for visits after Day 1. The predose concentrations will be summarized for each visit as part of the serum GDF-8 concentration data. In addition,  $C_{0(GDF-8)}$  will be summarized as a PD parameter for Day 1, and  $C_{trough(GDF-8)}$  will be summarized as a PD parameter for the last visit of each 16-week dose escalation level in Periods 1 and 2 as shown in the following table (with the Visits identified by Week).

Subjects	Visit(s)	Parameter	Analysis Scale	GDF-8
All Subjects	Week 1 (Day 1, prior to first dose)	$C_{0(GDF-8)}$	ln	D
	Weeks 13, 29, 45, 61, 77, 93 (Last dose for each dose escalation level in Periods 1 and 2)	$C_{trough(GDF-8)}$	ln	D

Key: D = Displayed with descriptive statistics, ln = natural log transformed.

The baseline for all pharmacodynamic endpoints is the last pre-dose value before the first dose.

### 3.3.3. Exploratory Endpoints

- *Changes from baseline in the Pediatric Data Outcomes Collection Instrument (PODCI) score as compared to placebo by Week 17, 33, and 49. Within subject change from baseline in the PODCI through Week 97.* The last pre-dose value will serve as the baseline for the PODCI questionnaire. The results will be presented by the Global Function score and the five domains: Upper Extremity and Physical Function; Transfer and Basic Mobility; Sports and Physical Functioning; Pain/Comfort and Happiness.

090177e1909dd632\Approved\Approved On: 25-Mar-2019 05:54 (GMT)

- *Mean percent change from baseline as compared to placebo in lean body mass by whole body DXA by Week 17, 33, and 49. Within subject from baseline in lean body mass through Week 97.*
- *Changes from baseline in muscle quality and fat fraction as compared to placebo as measured by T2-mapping and Dixon MRI Week 17, 33, and 49. Within subject change from baseline in T2-mapping and Dixon MRI at Week 97. Depending on the imaging capabilities at each site, this data may only be collected at a subset of sites.*

Specifically, these thigh MRI endpoints will include

- Whole Thigh Mean Fat Fraction, as measured by Dixon MRI, which is the mean fat fraction for the entire thigh muscle bundle (ie, muscle and inter/intra-muscular fat regions)
- Mean T2 relaxation time, which is the mean T2 value across the muscle bundle in a section of the thigh; and
- Percent Probable Muscle and Percent Probable Fat (ie, 100% - Percent Probable Muscle), which are derived from the T2 mapping acquisition.

Details of the thigh MRI measures are provided in the Study Imaging Review Charter.

- *Quantification of changes as measured by blood biomarkers (pharmacogenomic and liver).*
- *In subjects randomized to Sequences 1 and 2, duration of treatment response will be evaluated within subjects as compared to baseline for all efficacy (function and strength), pharmacologic and PD endpoints previously described through Week 97.*
- *In subjects randomized to Sequence 3, treatment response will be evaluated within subjects as compared to baseline for all efficacy (function and strength), pharmacologic and PD endpoints previously described through Week 97.*

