### **Statistical Method for Primary Efficacy**

The sample size is based on the primary endpoint of demonstrating efficacy of change from baseline on a 4 stair climb timed function test as compared to placebo at 49 weeks. To detect a 2.5 second difference in change from baseline in 4 stair climb based on a difference between the active treatment and the placebo treatment in Period 1 assuming a standard deviation of 4.0 with 80% power at  $\alpha=0.05$  (two-sided), a 2:1 treatment allocation and one IA, a total of 96 subjects should complete 49 weeks of dosing for this assessment. Assuming a 10% attrition rate, approximately 105 subjects should be enrolled (70 subjects receiving PF-06252616 and 35 subjects receiving placebo) in order to ensure a sufficient number of subjects will complete this assessment. If there are no safety issues and enrollment has completed, additional subjects may be enrolled prior to the time of the interim analysis. These additional subjects may help off-set any unforeseen variability that may occur outside the presumed standard deviation for this age group.

One IA is planned to evaluate futility and efficacy after approximately 50% of the subjects have completed through Week 49. Alpha- and beta-spending functions will be used to determine the cutoffs for efficacy and futility at the interim based on the observed number of subjects in the IA. The gamma family spending functions will be used to appropriately account for error spending and adjust for the observed information at the time of the IA and conservative boundaries ( $\gamma \leq -1$ ) will be used to define the futility and efficacy boundaries. The cutoff used at the IA will be calculated based on the percentage of subjects included at the IA to ensure appropriate protection of the type I error. Further details regarding the IA and simulations are included in the statistical analysis plan (SAP).

At the time of the IA if the E-DMC makes a recommendation to the sponsor management to modify or terminate the study based on establishing efficacy and safety of PF-06252616, the sponsor management will review the recommendation with regulatory agencies prior to making any changes to the study design, including termination of the study.

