### **2.2.4.3. Long Term Safety-Based on Data from Period 2**

In subjects randomized to Sequence 1, long term safety will be evaluated within subjects as compared to baseline for all safety endpoints previously described through Week 97.

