### **2.2.4.4. Duration of Treatment Response-Based on Data from Period 2**

In subjects randomized to Sequences 1 and 2, duration of treatment response will be evaluated within subjects as compared to baseline for all efficacy (function and strength), pharmacologic and PD endpoints previously described through Week 97.

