2	
In Section 2.1.2, two secondary objectives and endpoints have been added.
 
S6: To characterize the long-term effects following approximately 2-years of treatment with PF-06252616 on functional assessments compared to historical control.
 
S7: To characterize the effects of PF-06252616 on muscle strength and functional assessments compared to placebo in subset of subjects who may demonstrate a rapid disease decline and with relatively low variability over a one-year period (see Section 6.4 for the
	
 
The first objective was added to further describe how data from Sequence group 1 (subjects who will receive PF-06252616 in both Period 1 and 2 for approximately 2 years) will be evaluated for long-term efficacy. Upon review of additional Duchenne muscular dystrophy (DMD) natural history data of the 4 stair climb (4SC) which recently became available from 4 separate studies (The Cooperative International Neuromuscular Research Group [CINRG], University of Cincinnati [UofCCNT], University of Florida [UofFLA] and Leuven), the mean change in 4SC observed over 1 year was less (ranging from 0.9 to 1.99 seconds) in DMD patients who are 6 to <10 years old with a baseline 4SC of 2.5 to 12 seconds than originally estimated (~2.9 seconds) from the data available at the time when the protocol was first written. In addition, the natural history data showed that the 4SC time change over two years is approximately 4.3 seconds on average (in DMD patients who are 6 to <10 years old with a baseline 4SC of 2.5 to 12 seconds).
 

090177e1909dd632\Approved\Approved On: 25-Mar-2019 05:54 (GMT)

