### **6.3. Other Endpoint(s)**

*All exploratory endpoints, including the pharmacologic and health outcome endpoints, will be summarized by treatment group and period. Additional analyses may be performed to understand the relationship between these endpoints and treatment.*

Any population PK/PD analysis conducted will be reported separately.

Additionally, data permitting, relationships between PF-06252616 PK, GDF-8, imaging data (DXA, MRI), 4 stair climb, immunogenicity and any safety signals may be explored.

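### Withdrawal and continuation of treatment (E5) are evaluated by each boy's change from the pre-Day 1 baseline, and no randomised Sequence 1 versus Sequence 2 comparison is specified for Period 2

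*SAP*

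**What the plan says.** **E5.** SAP 3.3.3: "In subjects randomized to Sequences 1 and 2, duration of treatment response will be evaluated within subjects as compared to baseline", for function, strength, pharmacologic and PD endpoints to Week 97. Protocol 2.2.4.4 has the same rule. SAP 3.4 sets the functional baseline at the pre-dose baseline visit; no new baseline at Week 49 is defined.

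**E4.** Protocol 2.2.4.3: "In subjects randomized to Sequence 1, long term safety will be evaluated within subjects as compared to baseline". SAP 6.6 repeats this.

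**Period 2 displays.** SAP 6.3: "All exploratory endpoints, including the pharmacologic and health outcome endpoints, will be summarized by treatment group and period". Protocol 9.2.3 makes Period 2 analyses of the primary and secondary endpoints exploratory. SAP 5.2 allows displays by treatment group, sequence or period.

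**Design.** Boys are randomised to three sequences (Protocol 3.1). Sequences 1 and 2 have the same planned treatment through Week 45, then continue on drug or switch to placebo (Protocol Tables 3 and 4). Sites and subjects stay blinded to the end of the study. The 4 stair climb (4SC) is scheduled at Weeks 49, 57, 65, 73, 81, 89 and 97, with Week 49 in the pre-dose column.

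**Other Week 97 efficacy analyses.** Sequence 1 is compared with a historical control on 4SC, 6MWD, FVC and NSAA (SAP 6.2, 6.2.1). A cumulative plot of percent change in 4SC is drawn by sequence (SAP 6.1.2). MRI-to-4SC regressions may carry a sequence interaction (SAP 6.2).

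**The concern.** From Week 49, Sequences 1 and 2 differ by design only in drug versus placebo. That is a randomised, blinded withdrawal comparison, and its data are already scheduled for collection. The plan instead measures each boy against his own pre-Day 1 value. In a progressive disease that change contains two years of decline as well as any drug effect, so by itself it cannot say whether a boy in Sequence 2 lost a benefit or simply got older.

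The other Week 97 analyses do not fill the gap. The historical control covers only Sequence 1, is not randomised and says nothing about withdrawal. The plot by sequence gives no contrast and does not start from Week 49. At stake is whether E5 can be answered from this trial.

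**Working it through.** **1. The plan's own sample size.** Inputs are in the Protocol Summary and Protocol 9.1: "To detect a 2.5 second difference in change from baseline in 4 stair climb", "assuming a standard deviation of 4.0 with 80% power at" two-sided α = 0.05, with 2:1 allocation and one interim analysis. Fixed design:

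placebo n = 1.5 × 4.0² × (1.96 + 0.84)² / 2.5² ≈ 30.1, rounded up to 31; active 62; total 93.

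The interim analysis must be added. Using gamma-family spending at 50% information with gamma = −2 and non-binding futility (my assumption within the stated bound of −1 or lower), the inflation is 1.063, and 3 × 30.1 × 1.063 ≈ 96. The stated 96 is reproduced. Across gamma from −4 to −1 the total runs from about 92 to 100. Enrolment is 96/0.9 ≈ 107, against about 105 stated. The documents give no figure for Sequence 1 versus Sequence 2.

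**2. Natural decline.** SAP 1 gives 0.9 to 1.99 s over one year, and for two years "the natural history data showed that the 4SC time change over two years is approximately 4.3 seconds on average". Both apply to boys aged 6 to under 10 with baseline 4SC of 2.5 to 12 s.

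- Baseline to Week 97, the measure the plan uses: about 4.3 s.
- Second year alone: 4.3 − 1.99 = 2.31 s to 4.3 − 0.9 = 3.4 s, about the size of the 2.5 s target effect.

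**3. What an inactive drug would show.** Probability that within-boy change shows nominally significant worsening = Φ(mean/(SD/√n) − 1.96). The documents give no SD for change to Week 97, so I use 4.0 s (the sample-size assumption) to 7.5 s (the 12-month SD quoted in Protocol 1.10 for an earlier trial's placebo group). For n I use 35 (randomised), 32 (96/3) and 28 (assuming 20% attrition over two years).

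| Change | SD 4.0 | SD 7.5 |
|---|---|---|
| Baseline to Week 97, 4.3 s | about 100% | 86–92% |
| Second year, 2.31 s | 86–93% | 37–45% |
| Second year, 3.4 s | over 99% | 67–77% |

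In every row the expected Sequence 1 minus Sequence 2 difference is 0.

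**4. Precision of the randomised contrast.** SE = SD × √(2/n); half-width = 1.96 × SE.

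| n per arm | SD 4.0: half-width; power for 2.5 s | SD 7.5: half-width; power for 2.5 s |
|---|---|---|
| 35 | 1.87 s; 74% | 3.51 s; 29% |
| 32 | 1.96 s; 71% | 3.67 s; 27% |
| 28 | 2.10 s; 65% | 3.93 s; 24% |

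Eighty percent power for 2.5 s at SD 4.0 would need 41 per arm.

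**5. Carry-over.** Sequence 2's last active dose is at Week 45. Protocol 1.7 gives an adult half-life of up to 18 to 19 days at the higher doses. At 19 days, Week 57 is 84/19 ≈ 4.4 half-lives after that dose and Week 97 is 364/19 ≈ 19. Residual drug therefore matters mainly at early Period 2 visits.

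**The case against.** **Other comparisons exist.** A reader might infer that continuation and long-term safety are judged by within-boy change alone. The documents do not support that. Sequence 1 has the historical control as a secondary endpoint. Adverse events are compared with placebo by risk difference over the whole study, with an optional exposure-adjusted analysis (SAP 6.6.1). LVEF is compared with placebo, with shift tables by sequence (SAP 6.6.4). This stands, but none of these is a randomised estimate of continuing versus stopping.

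**Pooling is not a stated rule.** A reader might take SAP 6.3 to mean that Sequence 1 (second year of drug) and Sequence 3 (first year) are merged as active in Period 2. The wording permits that reading, but SAP 5.2 allows display by sequence and SAP 3.3.3 treats Sequence 3 separately. The text is ambiguous.

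**No false inference is written down.** The documents nowhere say that decline in Sequence 2 will be called lost response, and the same measure is reported in both sequences, so similar decline could be seen by eye. That is fair. But an informal side-by-side look gives no estimate or interval, and the option of additional analyses is not prespecification.

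**Natural-history figures.** Step 2 subtracts a one-year range across four studies from a single two-year average in boys under 10, while the trial enrols to under 16. The second-year figure is therefore rough. The argument does not depend on it: the planned measure runs from baseline, where 4.3 s applies directly.

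**The contrast has limits.** It is imprecise. Change from Week 49 omits boys who have already lost the test; since both arms had the same planned treatment until then, this narrows the population rather than favouring an arm, but loss after Week 49 may differ by arm. For E4, both arms had a year of drug, so a persisting first-year effect cancels. These points shape the fix; they do not make a confounded measure preferable.

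**Conclusion.** The concern holds in this form: E5 is evaluated by within-boy change from the pre-Day 1 baseline, and no randomised Sequence 1 versus Sequence 2 comparison is specified although the design supplies one. Ordinary decline of about 4.3 s over two years would make an entirely inactive drug show nominally significant within-boy worsening with probability of about 86% or more, under SDs of 4.0 to 7.5 s and 28 to 35 boys per arm. The randomised difference has expectation 0 in that case. The result rests on the SAP's natural-history averages applying to the enrolled boys and on an assumed SD for change to Week 97. It does not show that the sponsor would misread decline as lost response, or that Period 2 data will be pooled. The endpoints are exploratory, and the primary analysis is unaffected.

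**What to change.** In SAP 3.3.3 and 6.3:

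- **E5 estimate.** Add the exploratory difference Sequence 1 minus Sequence 2 with 95% CI, from the existing mixed model with sequence in place of treatment. Report change from baseline to Week 97, and change from Week 49 (with the Week 49 value as a covariate) to each Period 2 visit at which the endpoint is measured. Cover 4SC, the other function tests, strength, thigh muscle volume (MRI at Weeks 49 and 97 only) and lean body mass. Keep the within-subject summaries as description.
- **Loss of stair climbing.** For 4SC, also report velocity with 0 for boys unable to climb, as SAP 6.1.2 already does for the primary endpoint.
- **Carry-over.** Note that residual drug in Sequence 2 dilutes the early Period 2 contrasts.
- **Displays.** State that Period 2 summaries are shown by sequence.
- **E4.** The same pair may be shown as supportive, described as the effect of a second year of drug versus stopping after one, not the total long-term effect.

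Cost: SAP wording and a few extra model runs, with no new patients, visits or data. Protocol 9 and SAP 2 let the SAP modify planned analyses; only major changes to the primary endpoint or its analysis must also go into a protocol amendment. The price is a wide interval, so the result should be labelled an estimate and not a test.

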#### 2.1.3. Exploratory

- To evaluate biomarkers that may be informative in demonstrating the pharmacologic effect of PF-06252616.

- To evaluate biomarkers that may be informative for monitoring hepatic liver injury in the setting of dystrophic muscle.
- To evaluate the Functional Health Status.
- To evaluate long term safety of PF-06252616 in subjects treated for >1 year.
- To evaluate duration of treatment response following withdrawal and/or continuation of treatment for >1 year.
- To evaluate response in a delayed treatment group (Sequence Group 3, Period 2).

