### **4.3. Randomization Criteria**

Subjects will be randomized into the study provided they have satisfied all subject selection criteria. During the randomization, the results of the 4 SC from the baseline visit will be provided for stratification. Subjects will be stratified into two groups, those completing the 4 stair climb in  $\leq 8$  seconds and those completing in  $> 8$  seconds. Results from the *screening* 4 SC (not the baseline 4SC) will be used to determine subject's eligibility. The baseline 4SC will be used for all analysis.

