**6.2. Visit 2 (Baseline Day -4 up to -1 prior to dosing on Day 1)**

This visit *may* be conducted over 1 or 2 days as determined by the site.

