### **3.4. Baseline Variables and Covariates**

For all the primary and secondary functional endpoints, the baseline is defined as the last pre-dose assessment which is collected at the baseline visit.

Subjects will be stratified into two groups based on their ability to complete the 4 stair climb in  $\leq 8$  seconds or  $> 8$  second at baseline. This stratification factor may be used as a covariate in the statistical model when modeling data other than the 4 stair climb. For the 4 stair climb analysis, the actual baseline value instead of the stratification factor will be included in the model. The baseline value may also be included as a covariate in the model for the other functional, strength, or imaging assessments.

Additional covariates including the qualitative assessment for the 4SC will be summarized over time and may be explored in the modeling of the 4SC statistical analysis.

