**APPENDICES**

**Appendix 1. DATA DERIVATION DETAILS**

**Appendix 1.1. Definition and Use of Visit Windows in Reporting**

All windowing assignments will be reviewed by the study including any windowed visit with multiple observations more than 4 study days apart will be reviewed. Also any visits with no data will also be reviewed. Study windows may be adjusted to reflect appropriate data collection particular for the PK visits at weeks 2, 14, 18, 30, 34, and 46. The windowing definitions are included in Table 4. All windowing assignments are based on the relative study day. Relative study day 1 is always the first day of dosing.

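### Sequence 3 treatment response (objective E6) is measured from the pre-Day 1 baseline, so its Week 97 value mixes about 48 weeks of placebo change with about 48 weeks on active drug

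*SAP*

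**What the plan says.** The objective is stated in Protocol 2.1.3 as "To evaluate response in a delayed treatment group (Sequence Group 3, Period 2" and is repeated as E6 in the SAP. The heading of Protocol 2.2.4.5 ties the endpoint to Period 2 data. The endpoint itself, in that section and in SAP 3.3.3, is a within-subject comparison with baseline through Week 97: "In subjects randomized to Sequence 3, treatment response will be evaluated within subjects as compared to baseline". It covers all efficacy, pharmacologic and PD measures.

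Baseline is defined in these places:

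- SAP 3.4, functional endpoints: "the baseline is defined as the last pre-dose assessment which is collected at the baseline visit".
- Protocol 6.2 dates that visit: "Visit 2 (Baseline Day -4 up to -1 prior to dosing on Day 1".
- Protocol 4.3: "The baseline 4SC will be used for all analysis".
- SAP 3.3.2: "The baseline for all pharmacodynamic endpoints is the last pre-dose value before the first dose".
- SAP Appendix 1.1: "Relative study day 1 is always the first day of dosing". Protocol Section 5 counts placebo as investigational product, so Day 1 in Sequence 3 is a placebo day.

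Protocol Tables 3 and 4 put Sequence 3 on placebo from Week 1 to Week 45 and on active drug from Week 49. Neither document defines a Week 49 or Period 2 baseline. Protocol 9.2.3 and SAP 6.3 provide for summaries by period and leave room for further analyses, but they do not change the reference value.

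**The concern.** E6 asks what happens once active drug starts in boys who first had placebo. A change measured from before Day 1 includes everything that happened in the placebo period. In a progressive disease that is mostly decline, and the specified measure labels it treatment response. Read alone, a Week 97 value could suggest that delayed treatment failed when the boys had simply worsened before it began. What is at stake is the interpretation of one exploratory result. No hypothesis test, alpha, power or decision rule rests on E6.

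**Working it through.** The plan gives no target figure for E6, so there is none to reproduce. The check is which assessment serves as baseline, followed by arithmetic on the SAP's own natural-history values.

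**Decomposition.** Write Y0, Y49 and Y97 for a boy's 4SC time at baseline, at Week 49 before dosing, and at Week 97. The specified measure is

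Y97 − Y0 = (Y49 − Y0) + (Y97 − Y49).

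In Sequence 3 the first bracket is placebo change and the second is change on active drug. E6 concerns the second.

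**Inputs.**
- One-year natural-history change in 4SC: 0.9 to 1.99 s, the range over four studies (SAP Section 1).
- Two-year change, same section: "the 4SC time change over two years is approximately 4.3 seconds on average". Both figures are for ages 6 to under 10 with baseline 4SC of 2.5 to 12 s.
- Design effect, used only as a yardstick: 2.5 s (Protocol 9.1).

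**Placebo part.** 0.9 to 1.99 s. Scaled to 48 weeks it is 0.9 × 48/52 = 0.83 s to 1.99 × 48/52 = 1.84 s. Against the design effect it is 0.9/2.5 = 36% to 1.99/2.5 = 80%. Against the two-year untreated change it is 0.9/4.3 = 21% to 1.99/4.3 = 46%.

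**Implied second-year untreated change.** 4.3 − 0.9 = 3.4 s, or 4.3 − 1.99 = 2.31 s.

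**What each reference would show at Week 97** (positive means slower; the Period 2 effects are assumptions):

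| Period 2 effect | From Day 1 baseline | From Week 49 |
|---|---|---|
| None | 4.3 s | 3.4 to 2.31 s |
| All decline stops at Week 49 | 0.9 to 1.99 s | 0 s |
| 2.5 s benefit | 4.3 − 2.5 = 1.8 s | 3.4 − 2.5 = 0.9 s to 2.31 − 2.5 = −0.19 s |

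In each row the two columns differ by the placebo part.

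**Does re-baselining isolate the drug effect?** No. With an inert drug, a boy's Period 2 change would exceed his Period 1 change by 2.31 − 1.99 = 0.32 s to 3.4 − 0.9 = 2.5 s, because decline accelerates on these figures.

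**Are the Week 49 data there?** Yes. The Period 2 Schedule of Activities and Protocol 6.8 place functional tests, thigh MRI, whole-body DXA and PODCI at Visit 21. The SAP's Week 49 window runs from Day 320 to Day 351, past the planned Day 337 dose. The reference should therefore be defined as pre-dose, and not taken simply as the windowed Week 49 value.

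**The case against.** The strongest reply is that nothing is lost. The endpoint runs through Week 97 and is not a single number, and 4SC is scheduled at Weeks 49, 57, 65, 73, 81, 89 and 97. For boys with both values, (Y97 − Y0) − (Y49 − Y0) = Y97 − Y49, so Y0 cancels. A drug that stopped decline at Week 49 would appear as a flat line from there. The analysis is exploratory, and the existing wording already allows additional analyses.

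This stands as far as it goes. A reader might infer that the trial cannot answer E6, and the documents do not support that, because the needed change can be recovered from planned data. But the named endpoint is still change from the pre-Day 1 baseline, and recovering the relevant quantity is left to the reader or to an optional analysis.

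A reader might also infer that the same fault affects Sequence 2. It does not. The endpoint for Sequences 1 and 2 is duration of response, and a response is naturally judged from the state before treatment. Sequence 2 was on active drug until Week 49, so no placebo-year decline is carried forward. Change after withdrawal is a different question.

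Finally, neither obvious comparator for a Week 49 to 97 change is a clean control. A boy's own Period 1 change is confounded by accelerating decline, as shown above. Sequence 2 in Period 2 has just stopped active drug and is a withdrawal group. Boys who lose ambulation before Week 49 have no Week 49 4SC, because Protocol 7.8 stops its collection.

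**Conclusion.** The point holds for Sequence 3. As specified, the E6 measure combines a placebo period with an active period. On 4SC, about 0.9 to 1.99 s of worsening (0.83 to 1.84 s if scaled to 48 weeks) would be attributed to the active-treatment response.

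That size rests on three assumptions: that natural-history values for ages 6 to under 10 carry over to a trial enrolling ages 6 to under 16; that placebo boys decline at that rate; and, for the shares and second-year figures, that the one-year range and the two-year average describe comparable boys. The documents give no such figures for the other endpoints. Direction may differ too: SAP 6.2 allows for growth in thigh muscle volume, and growth in the placebo period could be credited to the drug. The pre-Day 1 baseline is explicit for functional and PD endpoints. It is not spelled out for DXA or the Dixon and T2 measures, although nothing suggests a Week 49 reference for them.

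A reader might infer that the efficacy conclusion of the trial is biased. It is not: the primary Week 49 comparison uses Period 1 data only and is unaffected.

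**What to change.** - In SAP 3.3.3 and 3.4, define for Sequence 3 a Period 2 baseline: the last assessment before the first Period 2 dose (Week 49, Visit 21). Report change from it through Week 97 as the E6 measure, and keep change from Day 1 as a secondary display.
- Align Protocol 2.2.4.5 and the Protocol 4.3 sentence on the baseline 4SC, so that the two documents agree.
- Handle boys who can no longer climb at Week 49 with the zero-velocity analysis already in SAP 5.3 and 6.1.2, and report how many there are.
- Label any comparison with a boy's own Period 1 change, or with Sequence 2 in Period 2, as descriptive. State that decline may accelerate in the second year and that Sequence 2 had just stopped active drug.
- Keep the Day 1 baseline for the duration-of-response endpoint in Sequences 1 and 2. Change from Week 49 in Sequence 2 is at most a supplementary display.

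The cost is SAP wording, one derived variable per endpoint and two aligned protocol passages. No new data collection is needed.
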